#### **6.4 STUDY INTERVENTION/EXPERIMENTAL MANIPULATION ADHERENCE**

Not applicable; participants of the POINT intervention or not required to adhere to any protocol.

#### **6.5 CONCOMITANT THERAPY**

Not applicable.

##### **6.5.1 RESCUE THERAPY**

Not applicable.

### **7 STUDY INTERVENTION/EXPERIMENTAL MANIPULATION DISCONTINUATION AND PARTICIPANT DISCONTINUATION/WITHDRAWAL**

#### **7.1 DISCONTINUATION OF STUDY INTERVENTION/EXPERIMENTAL MANIPULATION**

If a participant wishes to withdraw from the study, they can notify the Principal Investigators, Research Assistants, or Peer Recovery Coaches at any time. While there are no follow-up data collection activities with participants, participants are provided with the contact information for a Principal Investigator and the IRB and informed that they can make contact at any time to withdraw. Withdrawal from the study will not adversely affect the participant. If the participant is receiving POINT services, they will have the option to continue receiving them if they withdraw from the study. Should a participant withdraw, we will remove their data from the sample.

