## 4 STUDY DESIGN

### 4.1 OVERALL DESIGN

The primary objective of this pragmatic clinical trial is to replicate POINT at two new hospitals and establish POINT's effectiveness compared to standard care. In doing so, we aim to understand POINT's effect on the recovery process, including treatment and recovery outcomes and overdose. We hypothesize that POINT patients will engage in MOUD at higher rates, remain in treatment longer, and have significantly improved outcomes in comparison to the standard care group.

Hospital patients meeting the eligibility criteria at one of the two participating EDs are approached by a recovery coach or research assistant and invited to enroll in the study. Participants of the study are randomly enrolled into one of two study arms: (1) the POINT intervention arm, in which they receive ongoing recovery support services from a recovery coach or (2) the control arm, in which they receive a list of available local resources for substance use disorder from the research assistant. The study utilizes shift-level randomization, and each day of enrollment is separated into three enrollment shifts which are randomly assigned to one of the two study arms. Thus, participants' arm assignment is pre-determined by the shift in which they are discharged from the ED and enrolled into the study.

Participants are asked to complete a single structured interview at the time of their enrollment and are followed longitudinally only through administrative data, which is collected for participants from three years prior to their enrollment through two years following their enrollment.

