### 5.4 SCREEN FAILURES

Screen failures are defined as participants who consent to participate in this study but are not entered into the study because they do not meet the inclusion or exclusion criteria (i.e., failure of screening). If research staff or recovery coaches learn that the clinical information provided for someone previously consented to the study was inaccurate (for example, if a research staff member learns from a participant during their baseline assessment that their admission to the ED was non-opioid related and that the participant does not use opioids), data collection will be discontinued, and the participant will be excluded from the study. The patient will still be provided with the related study compensation for their time.

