#### **7.2 PARTICIPANT DISCONTINUATION/WITHDRAWAL FROM THE STUDY**

Participants are free to withdraw from participation in the study at any time upon request. An investigator may discontinue a participant from the study if the participant is later determined to not have originally met the inclusion criteria (e.g., admitted for an opioid-related reason). Subjects who have signed the informed consent form, and are randomized and receive the study intervention, and subsequently withdraw, or are discontinued from the study, will remain eligible to continue receiving recovery coach services.

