#### 8.3.4 TIME PERIOD AND FREQUENCY FOR EVENT ASSESSMENT AND FOLLOW-UP

The occurrence of an adverse event (AE) or serious adverse event (SAE) for participants receiving the POINT intervention may come to the attention of recovery coaches while performing follow-up engagement. However, the study relies on administrative data to follow participants longitudinally and does not allow study personnel to assess for adverse events in real-time.

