### 9.3 POPULATIONS FOR ANALYSES

All participants consented to the trial will be included in the analyses.

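### The plan says everyone consented is analysed, yet it removes people who withdraw or are found ineligible after allocation; the primary set is undefined, and the direction and size of any bias are unknown.

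*Combined protocol and SAP*

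**What the plan says.** Section 9.3 defines a single analysis population: "All participants consented to the trial will be included in the analyses". Sections 9.4.2 and 9.4.3 likewise name all study participants.

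Three other sections take people out after consent:

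- **Section 7.1 (withdrawal, at any time):** "Should a participant withdraw, we will remove their data from the sample".
- **Section 5.4 (ineligibility found after consent):** "If research staff or recovery coaches learn that the clinical information provided for someone previously consented to the study was inaccurate", then "data collection will be discontinued, and the participant will be excluded from the study".
- **Section 7.2 (investigator decision):** "An investigator may discontinue a participant from the study if the participant is later determined to not have originally met the inclusion criteria". The fate of the data is not stated.

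On timing, section 4.1 says that "participants' arm assignment is pre-determined by the shift in which they are discharged from the ED and enrolled into the study", and section 6.3 adds that shifts are assigned in advance. The only sensitivity analysis for the primary endpoint (9.4.2) concerns deaths. Section 8.3.6 monitors withdrawals and complaints for privacy and distress, but does not ask for counts by arm or reason.

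**The concern.** Two analysts following these sections would build different primary sets. One would keep everyone who consented; the other would drop withdrawals and late-found ineligibles. The second set is selected after allocation, so randomization by shift no longer protects it.

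The opportunity for removal is also unequal. Under 6.1.1 and 6.1.2, coaches contact POINT participants every 2-3 days at first and often work with them for weeks or months. Coaches are also one of the withdrawal routes in 7.1. Control participants receive a resource list and have no planned contact afterwards. Even at baseline, the 5.4 judgement falls to different staff in each arm, since 6.3 has coaches engage patients on POINT shifts and research assistants on control shifts; both know the arm.

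Outcomes come from administrative records pulled once 24 months have passed (Table 1) and need no further cooperation from the participant. Deleting a record is therefore a rule the plan chose rather than unavoidable missing data, and it can happen after the outcome has occurred. At stake is whether the primary comparison is by allocation at all.

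**Working it through.** **Inputs from the plan.** Control risk 12%, 6-point reduction, 80% power, 5% significance and 356 per arm (9.2); Fisher's exact test (9.4.2).

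**Assumptions, not in the documents.** A share *f* of the POINT arm is removed and nobody from control; those removed have overdose risk *r*; participants are independent. The 356 per arm is the planned size, which 9.2 says was not reached.

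**1. The plan's own figure.** With a pooled variance, two-sided and without continuity correction:

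n = [1.960·√(2·0.09·0.91) + 0.842·√(0.12·0.88 + 0.06·0.94)]² / 0.06² = (0.793 + 0.339)² / 0.0036 ≈ 356.

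This matches, so 12% against 6% is the right frame.

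**2. Observed POINT rate with no true effect.** Rate = (0.12 − f·r)/(1 − f). The last column is the exact probability that Fisher's test rejects at 5%, with 356 controls.

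| f (POINT kept) | r | Calculation | POINT rate | Rejects |
|---|---|---|---|---|
| 5% (338) | 0 | 0.120/0.95 | 12.6% | 5.2% |
| 5% (338) | 12% | 0.114/0.95 | 12.0% | 4.4% |
| 5% (338) | 30% | 0.105/0.95 | 11.1% | 6.0% |
| 5% (338) | 50% | 0.095/0.95 | 10.0% | 12.2% |
| 2% (349) | 0 | 0.120/0.98 | 12.2% | 4.4% |
| 2% (349) | 30% | 0.114/0.98 | 11.6% | 4.7% |
| 2% (349) | 50% | 0.110/0.98 | 11.2% | 5.6% |

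With nobody removed the test rejects 3.8% of the time. The rise to 4.4% at r = 12% comes from the discreteness of the test at unequal arm sizes, not from bias, so 4.4% is the benchmark for the other rows. At 1% removed, the rate stays between 0.120/0.99 = 12.1% (r = 0) and 0.115/0.99 = 11.6% (r = 50%).

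**3. With the planned effect (12% against 6%) and 5% removed.** If r = 0, the POINT rate is 0.06/0.95 = 6.3% and the difference is 5.7 points. If r = 24%, it is (0.06 − 0.012)/0.95 = 5.05% and the difference is about 6.9 points.

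**4. What a bound could recover.** If *d* of 356 POINT records are deleted and *x* events remain, the full-arm rate lies between x/356 and (x + d)/356. The width is d/356: 7/356 = 2.0 points at 2% removed and 18/356 = 5.1 points at 5%.

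**The case against.** The strongest reply is that 9.3 can be read as subject to 7.1: everyone consented, less those who asked to leave. That removes the literal contradiction but not the problem, because the resulting set is still selected after allocation and nothing counts or bounds the loss.

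Several stronger readings are tempting, and the documents do not support them.

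- **That removals do fall mainly in the POINT arm.** No section says so. Section 7.1 gives all participants an investigator's and the IRB's contact details, and the competency check in 8.1 makes every enrollee state how to withdraw. Section 5.4 names both kinds of staff, and its example arises in the baseline interview, which both arms complete. The remark in 8.3.4 that events "may come to the attention of recovery coaches while performing follow-up engagement" is about adverse events, not withdrawal or ineligibility. Unequal planned contact supports *may*, no more.
- **That people who disengage or relapse drop out of the analysis and so flatter POINT.** Section 7.3 lets participants stop seeing the coach and does not remove them. They are followed through records unless they ask to leave the study, and 7.1 allows services to continue even then.
- **That 7.2 deletes data.** It speaks of discontinuation and is silent on data.
- **That the result hinges on a single record.** One can find a table where it does: 43/356 against 27/356 gives p = 0.058, and deleting one POINT participant with an event gives 0.042. But 26/356 with nobody deleted also gives 0.042. That shows the coarseness of Fisher's test near the threshold, not removal bias.

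It is also fair to say that removal from POINT alone and a risk of 30-50% among those removed are assumptions, and that 50% is an extreme one. Retaining data after withdrawal depends on the consent form, which is not among the documents reviewed.

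**Conclusion.** The point stands in a limited form. Sections 5.4 and 7.1 cannot be followed together with 9.3 as written, 7.2 leaves the data question open, and the removals come after allocation without any count by arm or sensitivity analysis.

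Whether this biases the result, and which way, cannot be known from the documents. Under the stated assumptions, removing 5% of POINT alone moves a null comparison by between +0.6 points (r = 0) and −2.0 points (r = 50%), against a 6-point target. Removing 1-2% moves it by at most 0.8 points (12.0% to 11.2%) over the same range of risk. If those removed have their arm's average risk, the shift is zero. The plan should be corrected, but this is not evidence that the trial's comparison is wrong.

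**What to change.** 1. **Section 9.3:** make the primary set everyone consented, analysed by the arm of the enrollment shift, and align 5.4, 7.1, 7.2, 9.4.2 and 9.4.3 with it.
2. **Section 7.1:** where the consent form allows, let withdrawal mean no further data linkage with data to date kept, and make deletion a separate request.
3. **Sections 5.4 and 7.2:** exclude for ineligibility only on information recorded before enrollment (the index ED record and the screening score), by the same rule in both arms and, where feasible, by someone masked to arm. State in 7.2 what happens to the data.
4. **Reporting:** give removals by arm, reason and timing, and add a best/worst-case bound for deleted records as a sensitivity analysis.

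The cost is mainly wording, plus a check of the consent form. A few ineligible people will stay in the primary set and dilute the effect slightly. The note in 9.2 indicates that the planned analyses have already been run, so records already deleted can be counted and bounded but not restored. At 5% deleted the bound is nearly as wide as the target effect, so retaining data wherever consent permits is worth more than bounding its loss.

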#### **7.2 PARTICIPANT DISCONTINUATION/WITHDRAWAL FROM THE STUDY**

Participants are free to withdraw from participation in the study at any time upon request. An investigator may discontinue a participant from the study if the participant is later determined to not have originally met the inclusion criteria (e.g., admitted for an opioid-related reason). Subjects who have signed the informed consent form, and are randomized and receive the study intervention, and subsequently withdraw, or are discontinued from the study, will remain eligible to continue receiving recovery coach services.

### 7.3 LOST TO FOLLOW-UP

Study participants are involved in data collection activities at a single time (i.e., enrollment) and do not participate in any follow-up data collection. Participants of the intervention arm are not required to engage in further interactions with the recovery coach; thus, participants can disengage whenever they prefer.

## 8 STUDY ASSESSMENTS AND PROCEDURES

### 8.1 ENDPOINT AND OTHER NON-SAFETY ASSESSMENTS

The study will utilize the following procedures, measures, and assessments during the eligibility screening and data collection processes.

Prior to recruitment, a research assistant or recovery coach will (a) verify that patients are at least 18 years of age and (b) have been admitted to the ED for an opioid-related reason. Additionally, prior to screening the patient for eligibility, it must be confirmed that (c) a patient is cleared for discharge from the ED by a healthcare provider; this may include patients who are discharged from the ED but admitted to inpatient care and those returning home. To do so, the research assistant or recovery coach will first approach the ED staff and ask if the patient is medically cleared for discharge. If so, the patient may be approached by the study team member.

Subsequently, the research assistant or recovery coach will utilize a recruitment script to introduce themselves and the study and (d) assess the patient for an opioid use disorder by reading the questions from the *DSM-5 Criteria for Diagnosis of Opioid Use Disorder* to the patient. A score of at least "1" is required for eligibility. Lastly, they will read the statement of informed consent to the participant if they are interested in the study and will confirm the final component of eligibility by (e) reading three questions to the patient to confirm the patient's competency: (1) Can you repeat to me the purpose of the study? [Response: The patient must say something indicating they know we are interested in studying opioid use and/or overdose.] (2) Do you remember some of the types of data we will be collecting about you or the agencies we will be getting them from? [Response: The patient must name at least two data sources.] (3) Do you remember what you should do if you decided you no longer wish to take part in the study after leaving here? [Response: The patient must indicate that they can call the research team or IRB and let them know.] If the patient does not answer correctly, the research team member will attempt to re-explain the consent form and ask the questions a second time. If the patient still does not answer correctly, the patient is not eligible for the study.

If the patient meets all criteria and consents to enrollment, the patient will be asked to immediately complete a structured interview that asks questions regarding the patient's:

1. Demographics

2. Social support
3. Living arrangements
4. Drug use
5. Context of current overdose or ED admission
6. Treatment history
7. Interest in recovery services
8. Use of strategies to reduce risks related to drug use
9. HIV and Hepatitis C
10. Physical and mental health

The patient will also be asked to complete the Adverse Childhood Experiences questionnaire.

In addition to the original data collection, administrative data will be collected for each participant to assess long-term impacts regarding health, treatment, criminal justice, and child welfare involvement, as well as death records. Secondary data collection for the study will be assessed accessed from the following sources for three years prior to a participant's enrollment through two years following:

1. Indiana Network for Patient Care (*hospital and overdose admissions data*)
2. Indiana Scheduled Prescription Electronic Collection & Tracking Program (INSPECT) (*prescription information for controlled substances*)
3. Division of Mental Health and Addiction (*methadone treatment information*)
4. Indiana Office of Medicaid Planning and Policy (*Medicaid enrollment information*)
5. Indiana Department of Child Services (*child welfare involvement information*)
6. Publicly available arrest and incarceration data via (a) Indiana Department of Correction's prison incarceration search portal and (b) Marion County's inmate database search portal
7. Indiana Department of Public Health Vital Records Data (*state health/vital records*)

## 8.2 SAFETY ASSESSMENTS

Not applicable.

## 8.3 ADVERSE EVENTS AND SERIOUS ADVERSE EVENTS

### 8.3.1 DEFINITION OF ADVERSE EVENTS

This protocol uses the definition of adverse event from 21 CFR 312.32 (a): any untoward medical occurrence associated with the use of an intervention in humans, ***whether or not considered intervention related.***

These will include the following as pertains to the study: violation of confidentiality; discomfort due to interview procedures (including embarrassment in disclosing sensitive information); and disclosure of information about current or intended physical harm to self or others.

### 8.3.2 DEFINITION OF SERIOUS ADVERSE EVENTS

An adverse event (AE) or suspected adverse reaction is considered "serious" if it results in any of the following outcomes: death, a life-threatening adverse event, inpatient hospitalization or prolongation of existing hospitalization, a persistent or significant incapacity or substantial disruption of the ability to conduct normal functions, or a congenital anomaly/birth defect. Important medical events that may not result in death, be life-threatening, or require hospitalization may be considered serious when, based upon appropriate medical judgment, they may jeopardize the participant and may require medical or surgical intervention to prevent one of the outcomes listed in this definition.

These will include the following: death; subsequent hospitalizations; and any other conditions or situations members of the DSMB believe represent serious adverse events that can be measured with the available data.

### 8.3.3 CLASSIFICATION OF AN ADVERSE EVENT

#### 8.3.3.1 SEVERITY OF EVENT

For adverse events (AEs) not included in the protocol defined grading system, the following guidelines will be used to describe severity.

- **Mild** – Events require minimal or no treatment and do not interfere with the participant's daily activities.
- **Moderate** – Events result in a low level of inconvenience or concern with the therapeutic measures. Moderate events may cause some interference with functioning.
- **Severe** – Events interrupt a participant's usual daily activity and may require systemic drug therapy or other treatment. Severe events are usually potentially life-threatening or incapacitating. Of note, the term "severe" does not necessarily equate to "serious".]

#### 8.3.3.2 RELATIONSHIP TO STUDY INTERVENTION/EXPERIMENTAL MANIPULATION

All adverse events (AEs) will have their relationship to study procedures, including the intervention, assessed by an appropriately trained clinician based on temporal relationship and his/her clinical judgment. The degree of certainty about causality will be graded using the categories below.

- **Related** – The AE is known to occur with the study procedures, there is a reasonable possibility that the study procedures caused the AE, or there is a temporal relationship between the study procedures and the event. Reasonable possibility means that there is evidence to suggest a causal relationship between the study procedures and the AE.
- **Not Related** – There is not a reasonable possibility that the study procedures caused the event, there is no temporal relationship between the study procedures and event onset, or an alternate etiology has been established.

OR

- **Definitely Related** – There is clear evidence to suggest a causal relationship, and other possible contributing factors can be ruled out. The clinical event, including an abnormal laboratory test result, occurs in a plausible time relationship to study procedures administration and cannot be

explained by concurrent disease or other drugs or chemicals. The response to withdrawal of the study procedures should be clinically plausible. The event must be pharmacologically or phenomenologically definitive.

- **Probably Related** – There is evidence to suggest a causal relationship, and the influence of other factors is unlikely. The clinical event, including an abnormal laboratory test result, occurs within a reasonable time after administration of the study procedures, is unlikely to be attributed to concurrent disease or other drugs or chemicals, and follows a clinically reasonable response on withdrawal.
- **Potentially Related** – There is some evidence to suggest a causal relationship (e.g., the event occurred within a reasonable time after administration of study procedures). However, other factors may have contributed to the event (e.g., the participant's clinical condition, other concomitant events). Although an AE may rate only as "possibly related" soon after discovery, it can be flagged as requiring more information and later be upgraded to "probably related" or "definitely related", as appropriate.
- **Unlikely to be related** – A clinical event, including an abnormal laboratory test result, whose temporal relationship to study procedures administration makes a causal relationship improbable (e.g., the event did not occur within a reasonable time after administration of the study procedures) and in which other drugs or chemicals or underlying disease provides plausible explanations (e.g., the participant's clinical condition, other concomitant treatments).
- **Not Related** – The AE is completely independent of study procedures administration, and/or evidence exists that the event is definitely related to another etiology. There must be an alternative, definitive etiology documented by the clinician.

